The 7- and 9-point SMPG profiles will be used for titration purposes and evaluation of the effect of the trial. The subject will be instructed to perform a 7-9-7 point profile on the 3 consecutive days just before selected visits as outlined in the flowchart in section $\underline{2}$. See $\underline{\text{Table 8-2}}$ (7-point profiles indicated as X and the 9-point profile indicated as $\sqrt{ }$).

Protocol Da	Date: 23 February 2018	Novo Nordisk
-------------	------------------------	--------------

 Trial ID: NN1218-4113
 Version: 4.0

 UTN: U1111-1180-0636
 Status: Final Page: 46 of 112

Table 8–2 7-point SMPG profiles with additional 9-point SMPG profile

Time point	Day -3 7-point profile	Day -2 9-point profile	Day -1 7-point profile
Before breakfast	X	1/	√(X) ^a
60 minutes after the start of breakfast	X	1/	X
Before lunch	X	1/	X
60 minutes after the start of lunch	X	1/	X
Before main evening meal	X	1/	X
60 minutes after the start of main evening meal	X	1/	X
At bedtime	X	1/	X
At 4 am		1/	

^aThe last SMPG in the 9-point profile and the first SMPG of the 7-point profile on day-1 are overlapping.

For SMPG measurements actual clock time, time point (e.g. before breakfast), date and value should be recorded in the diary. SMPG values measured before breakfast, lunch and main evening meal and at bedtime should be performed before any insulin injection and just before the start of the meal (breakfast, lunch or main evening meal). SMPG values measured before breakfast should be performed in a fasting condition.

The measurements will be used to evaluate the glucose profile.

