2.1 Sample size calculation

The sample size is determined to ensure a sufficient power for step 1 and step 2 in the hierarchical testing procedure for the primary estimand presented in section $\underline{2}$. The power for step 3 and 4 in the hierarchical testing procedure will also be presented. The sample size is determined using a non-inferiority limit of 0.4% in step 1, which was chosen as described in section 5.2.1 in the protocol. The statistical evaluation will be done as described in sections $\underline{2.3}$ and $\underline{2.4}$.

In previous confirmatory trials where faster aspart has been investigated, the completion rates have been high. Therefore it will be expected that treatment discontinuation might be as low as 10% where trial discontinuation constitutes half of these and with similar withdrawal reasons in the treatment arms.

Power for the non-inferiority step (Step 1) is based on a t-statistic under the assumption of a one-sided test of size 2.5% for the FAS. A mean treatment difference of -0.1% for the comparison between faster aspart and NovoRapid[®] in favour of faster aspart is expected. As trials in this population where data from treatment withdrawn subjects is retrieved is limited, a conservative estimate of the standard deviation (SD) in change from baseline in HbA_{1c} of 0.8% was chosen. The power for superiority in step 3 will be calculated using the same assumptions as for step 1 but without the non-inferiority margin.

For determination of power in step 2 in the hierarchical testing, where change from baseline in 1-hour PPG increment 16 weeks after randomisation is compared between faster aspart and NovoRapid® a t-statistic with a two-sided test of size 5% is used, where the treatment difference is

Statistical Analysis Plan		Date:	12 February 2019	Novo Nordisk
Trial ID: NN1218-4113	CONFIDENTIAL	Version:	2.0	
UTN: U1111-1180-0636	CONFIDENTIAL	Status:	Final	
EudraCT No.: 2016-000878-38		Page:	9 of 29	

expected to be at least 0.6 mmol/L [11 mg/dL]. The SD=3.5 mmol/L [63 mg/dL] in change from baseline in 1-hour PPG increments 16 weeks after randomisation based on laboratory analysed PG in a standardised meal test will be considered reasonable based on trials NN1218-3852 and NN1218-3853.

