2.4.2 Supportive secondary endpoints

2.4.2.1 Efficacy endpoints

All endpoints except insulin dose in this section will be assessed using the FAS and the in-trial observation period and repeated using the on-treatment observation period. Insulin dose will be presented using the safety analysis set and will therefore only use the on-treatment observation period.

Change from baseline in FPG 16 weeks after randomisation

Change from baseline in FPG 16 weeks after randomisation will be analysed based on all planned post baseline measurements until or at 16 weeks after randomisation using a model similar to 1) except with baseline FPG as covariate.

If a subject achieves HbA_{1c} target 16 weeks after randomisation

$HbA_{1c} < 7.0\%$

A dichotomous (responder/non-responder) endpoint will be defined based on whether a subject has met the HbA_{1c} target ($HbA_{1c} < 7.0\%$) 16 weeks after randomisation.

This responder endpoint will be analysed based on a logistic regression model using treatment, region and metformin use at baseline (Yes/No) as factors, and baseline HbA_{1c} as covariate. In analysis of the in-trial observation period subjects without an HbA_{1c} measurement at week 16 will be treated as non-responders. In the analysis using the on-treatment observation period subjects who discontinue randomised treatment, initiate ancillary treatment, withdraw from trial, and/or have no HbA_{1c} measurement at week 16 are included as non-responders.

Statistical Analysis Plan Trial ID: NN1218-4113 UTN: U1111-1180-0636 EudraCT No.: 2016-000878-38

CONFIDENTIAL

Date: Version: Status: Page:

12 February 2019 | Novo Nordisk Final 18 of 29

$HbA_{1c} < 7.0$ % without severe hypoglycaemia

A dichotomous (responder/non-responder) endpoint will be defined based on whether a subject has met the HbA_{1c} target (HbA_{1c} <7.0%) 16 weeks after randomisation without treatment emergent severe hypoglycaemic episodes.

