separate profile. The mean of the derived increments will then be calculated separately for each meal. Mean 1 hour PPG increments over all meals will be derived as the mean of all corresponding mean meal increments.

• Change from baseline in mean of the 7-9-7-point SMPG profile

The mean of the 7-9-7-point SMPG profile is defined as the area under the curve profile divided by the measurement time, and is calculated using the linear trapezoidal technique.

Change from baseline in the mean of the 7-9-7-point SMPG profile 16 weeks after randomisation will be analysed based on all planned post baseline measurements until or at 16 weeks after randomisation using a model similar to 1) except with the corresponding baseline value as covariate.

• Change from baseline in PPG and PPG increment (mean, breakfast, lunch and main evening meal)

Change from baseline in PPG and PPG increment endpoints 16 weeks after randomisation for mean over all three meals and the individual meals will be analysed separately based on all planned post baseline measurements until or at 16 weeks after randomisation using a model similar to 1) except with the corresponding baseline value as covariate.

• Fluctuation in 7-9-7-point SMPG profile

The fluctuation in the 7-9-7-point SMPG profile is defined as:

$$\frac{1}{T} \int_{0}^{T} |PG(t) - \overline{PG}| dt$$

where T, PG(t) and \overline{PG} denotes the length of the profile, the PG value at time t and the mean of the profile, respectively. It will be calculated using the linear trapezoidal technique.

Fluctuation in the 7-9-7-point SMPG profile will be logarithmically transformed and analysed based on all planned post baseline measurements until or at 16 weeks after randomisation using a model similar to 1) except with the corresponding log-transformed baseline value as covariate. Estimated treatment means and the estimated treatment differences with corresponding 95% CI will be back-transformed to the original scale, resulting in estimated geometric means, a treatment ratio and a 95% CI for the treatment ratio.

• Change from baseline in nocturnal SMPG measurements

Statistical Analysis Plan		Date:	12 February 2019	Novo Nordisk
Trial ID: NN1218-4113	CONFIDENTIAL	Version:	2.0	
UTN: U1111-1180-0636	CONFIDENTIAL	Status:	Final	
EudraCT No.: 2016-000878-38		Page:	20 of 29	

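### Read plainly, the trapezoidal rule for SMPG fluctuation does not return the integral that the SAP defines wherever the profile crosses its mean, and the SAP does not say how such segments are handled

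*SAP*

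**What the plan says.** SAP 2.4.2.1 introduces the endpoint with "The fluctuation in the 7-9-7-point SMPG profile is defined as" and gives (1/T)∫|PG(t) − mean| dt from 0 to T, where T is the length of the profile. The next sentence is "It will be calculated using the linear trapezoidal technique". Protocol version 4.0, section 17.4.2.1, has the same formula and the same rule.

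The profile mean, a few lines earlier in the SAP, "is defined as the area under the curve profile divided by the measurement time, and is calculated using the linear trapezoidal technique". For the mean, that amounts to joining the measured glucose values by straight lines.

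Table 8–2 in Protocol 8.3.3 fixes the sampling: before each main meal, an hour after it starts (for example "60 minutes after the start of breakfast"), and at bedtime. The middle day adds a 4 am value and the next pre-breakfast value.

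For the analysis, "Fluctuation in the 7-9-7-point SMPG profile will be logarithmically transformed and analysed", with log baseline as covariate, "resulting in estimated geometric means, a treatment ratio and a 95% CI for the treatment ratio". The endpoint sits under "2.4.2 Supportive secondary endpoints", outside the four-step testing hierarchy.

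**The concern.** The quantity to be integrated is the absolute deviation, and the trapezoidal rule is named as the way to integrate it. A programmer following the text would take |PG − mean| at each sample and join those values by straight lines. That treats glucose as never passing through its mean between a low pre-meal value and a high post-meal value. The straight-line glucose profile used for the mean does pass through it. The mean and the deviation from it would then rest on two different curves.

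This puts two things at stake. The reported geometric means may not be the defined quantity, and two competent programmers could report materially different values from the same data. Moreover, the error depends on where the peaks lie relative to the mean. Faster aspart is intended to lower those peaks, so the error need not be proportionally equal in both arms and need not cancel in the ratio.

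**Working it through.** **No stated figure to reproduce.** Neither document gives a fluctuation value, an SMPG profile, measurement times or an SMPG variance. The formula, rule, sampling pattern and log scale come from the documents; every glucose value, time and SD below is an assumption.

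**One segment.** Let the profile run over h hours from a below the mean to b above it. The straight line crosses the mean after h·a/(a+b) hours, which leaves two triangles:

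- Linear profile: ½·a·[h·a/(a+b)] + ½·b·[h·b/(a+b)] = h(a²+b²)/(2(a+b))
- Rule on sampled absolute deviations (node-wise): h(a+b)/2
- Node-wise ÷ linear profile: (a+b)²/(a²+b²)

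This ratio is 2 when a = b, 1.8 when one deviation is half the other, 1.47 at a quarter and 1.20 at a tenth. Segments that do not cross agree exactly. No segment is understated, so errors within a profile cannot offset each other.

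**Worked 9-point day.** Assumed values are 6.0, 9.5, 7.0, 9.0, 7.5, 9.0, 8.5, 7.0 (4 am) and 6.0 mmol/L at 0, 1, 5, 6, 11, 12, 15.5, 21 and 24 h. The area under the profile is 191.0, so the mean is 191.0/24 = 7.958.

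| Segment (h) | Deviations | Node-wise | Linear profile |
|---|---|---|---|
| 0–1 | −1.958, 1.542 | 1.750 | 0.887 |
| 1–5 | 1.542, −0.958 | 5.000 | 2.636 |
| 5–6 | −0.958, 1.042 | 1.000 | 0.501 |
| 6–11 | 1.042, −0.458 | 3.750 | 2.159 |
| 11–12 | −0.458, 1.042 | 0.750 | 0.432 |
| 12–15.5 | 1.042, 0.542 | 2.771 | 2.771 |
| 15.5–21 | 0.542, −0.958 | 4.125 | 2.222 |
| 21–24 | −0.958, −1.958 | 4.375 | 4.375 |
| Sum | | 23.521 | 15.982 |

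Dividing by 24 gives 0.980 against 0.666 (+47%). The first seven points alone (T = 15.5 h, mean 8.315) give 13.774/15.5 = 0.889 against 7.813/15.5 = 0.504 (+76%).

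**Range of overstatement.**

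- *Six other fixed profiles* (07:30, 08:30, 12:30, 13:30, 18:30, 19:30, 22:30, 04:00, next breakfast): 41–67% for the continuous 7-9-7 series, 54–100% for a 7-point day, 29–57% for a 9-point day.
- *Noisy simulations at those times* (point SD 0.8, 1.5, 2.2 mmol/L): 28–35% for 7-9-7, 39–56% for a 7-point day, about 30% for a 9-point day.
- *Worked profile with noise* (between-subject SD 1.0, point SD 0.8 to 2.2): 34–48% if fluctuation is computed by day and averaged, 29–40% if the three days form one series.

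**Treatment ratio with one-hour peaks 0.6 mmol/L lower.** The 0.6 is the planning difference for the meal-test one-hour increment in SAP 2.1, carried over to SMPG as an assumption.

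| Case | Node-wise | Linear profile |
|---|---|---|
| Worked profile, SD 1.6, one series | 0.937 | 0.949 |
| Worked profile, SD 1.6, daily averaging | 0.930 | 0.952 |
| Simulated 7-9-7, SD 0.8 | 0.856 | 0.879 |
| Simulated 7-9-7, SD 1.5 | 0.919 | 0.935 |
| Simulated 7-9-7, SD 2.2 | 0.953 | 0.963 |
| Fixed 7-9-7, steeply rising pre-meal, high bedtime | 0.814 | 0.845 |
| Fixed 7-9-7, pure zigzag | 0.800 | 0.800 |
| Fixed 7-9-7, flat 6.5 pre-meal | 0.778 | 0.755 |

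The ratio moved further from 1 in every noisy simulation. Among the six fixed 7-9-7 profiles it moved further from 1 in three, was unchanged in one and moved closer in two.

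**The case against.** The strongest reply is that the SAP never says the rule is applied to sampled absolute deviations. It names the same technique for the profile mean. Interpolating PG(t) linearly and then integrating |PG(t) − mean| exactly fits the text and carries no such error. This stands: a reader might infer that the SAP prescribes a wrong calculation, but the documents show only that the plain reading is wrong and that the alternative is not stated.

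A reader might also settle on a single figure, such as 40% overstatement, or conclude that the treatment benefit is inflated by about half. Neither is documented. The second comes from one assumed profile with daily averaging, where the reduction is about 7.0% against 4.8%. As one continuous series, the same assumptions give 6.3% against 5.1%, about a quarter larger. SAP 2.4.2.1 says analyses are in general based on the entire 7-9-7 profile, which leans towards the continuous series without settling the matter.

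Nor does the error always favour faster aspart. A proportional error common to both arms cancels on the log scale, and two fixed profiles showed attenuation. If both arms have the same glucose distribution, either rule gives an expected log ratio of zero, so the choice does not by itself create a treatment difference.

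Finally, with seven to nine samples a day, the linear profile only approximates true glucose. That is fair, but it is the approximation the plan itself uses for the mean, so it is the right benchmark for consistency.

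**Conclusion.** The point holds as a flaw in specification. On its plain reading, the stated rule does not deliver the stated formula: every segment crossing the mean is overstated by a factor between 1 and 2, and the sampling scheme makes such segments common. This part is algebra and holds whether T is one day or three.

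The size rests on assumed profiles, times and noise: roughly 30–65% for the 7-9-7 series and up to 100% for a single 7-point day. The effect on the treatment ratio is usually a modest shift away from 1 when one-hour peaks differ, about 0.01 to 0.02 in the simulated 7-9-7 cases, but it can be nil or reversed.

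The geometric means are therefore at greater risk than the ratio. The consequence is confined to this supportive endpoint; the primary analysis, the confirmatory hierarchy and the safety analyses are untouched. The correction is still worth making, because it is almost free and settles what will be reported.

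**What to change.** In SAP 2.4.2.1, replace the sentence naming the technique for fluctuation with:

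*PG(t) is the linear interpolation between measurements; the time at which it crosses the profile mean is added as a node in each segment before the trapezoidal rule is applied to |PG(t) − mean|.*

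In the same place, state whether T is each daily profile (with the daily values then averaged) or the whole three-day series.

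The cost is two sentences and a few lines of code. No new data are needed, since Protocol 8.3.3 already has clock times recorded for each SMPG value. The endpoint definition, log-scale model and reported contrast stay as they are. If the existing programs already split segments at the mean, the new text simply documents it.

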2.4.2.2 Safety endpoints

In terms of AEs, as a minimum, SAEs will be tabulated separately using the in-trial observation period.

All events in the in-trial observation period will be listed with information about whether it appeared in the on-treatment observation period or not.

Number of treatment emergent adverse events

Adverse events (AEs) will be coded using the Medical Dictionary for Regulatory Activities (MedDRA). AEs will be presented based on system organ class and preferred terms.

A Treatment Emergent Adverse Event (TEAE) is defined as an event that has an onset date on or after the first day of exposure to randomised treatment, and no later than seven days after the last day of exposure to randomised treatment.

TEAEs are summarised descriptively, whereas AEs not defined as treatment emergent are presented in listings, including AEs reported in the 30-day follow-up period. The summaries of TEAEs are made displaying the number of subjects with at least one event, the percentage of subjects with at least one event, the number of events and the event rate per 100 patient years of exposure. These summaries are done by seriousness, severity, relation to insulin treatment, relation to technical complaint, premature treatment discontinuation due to AEs, and outcome.

Furthermore, summary tables based on system organ class and preferred terms are made for:

All TEAEs

- Serious TEAEs
- Possibly or probably related TEAEs
- Severe TEAEs
- TEAEs with preferred term that are experienced by at least 5% of the subjects in any treatment arm or by at least 5% of all subjects

For AEs where additional information is recorded, this will be listed.

AEs occurring during the run-in period are considered non-treatment emergent and will be summarised separately.

Number of treatment emergent injection site reactions

Treatment emergent injection site reactions occurring during the trial will be summarised and listed.

Classification of Hypoglycaemia

Treatment emergent: hypoglycaemic episodes will be defined as treatment emergent if the onset of the episode occurs on or after the first day of exposure to randomised treatment, and no later than one day after the last day of exposure to randomised treatment.

Nocturnal hypoglycaemic episodes: episodes occurring between 00:01 and 05.59 both inclusive.

[figure not shown]
Hypoglycaemic episodes are classified according to the Novo Nordisk classification of hypoglycaemia (see Figure 2–1) and the ADA classification of hypoglycaemia (see Figure 2–2).

Novo Nordisk classification of hypoglycaemia

In normal physiology, symptoms of hypoglycaemia occur below a PG level of 3.1 mmol/L (56 mg/dL). Therefore, Novo Nordisk has included hypoglycaemia with PG levels below this cut-off point in the definition of BG confirmed hypoglycaemia.

Novo Nordisk uses the following classification (see Figure 2–1) in addition to the ADA classification:

- Severe hypoglycaemia according to the ADA classification.⁴
- Severe or BG confirmed hypoglycaemia: An episode that is severe according to the ADA classification⁴ or BG confirmed by a PG value <3.1 mmol/L (56 mg/dL) with or without symptoms consistent with hypoglycaemia.

[figure not shown]
Note: Glucose measurements are performed with capillary blood calibrated to plasma equivalent glucose values

BG: blood glucose PG: plasma glucose SMPG: Self-measured plasma glucose

Figure 2–1 Novo Nordisk classification of hypoglycaemia

ADA classification⁴ of hypoglycaemia

- Severe hypoglycaemia: An episode requiring assistance of another person to actively administer carbohydrate, glucagon, or take other corrective actions. Plasma glucose concentrations may not be available during an event, but neurological recovery following the return of PG to normal is considered sufficient evidence that the event was induced by a low PG concentration.
- Asymptomatic hypoglycaemia: An episode not accompanied by typical symptoms of hypoglycaemia, but with a measured PG concentration ≤ 3.9 mmol/L (70 mg/dL).
- Documented symptomatic hypoglycaemia: An episode during which typical symptoms of hypoglycaemia are accompanied by a measured PG concentration ≤ 3.9 mmol/L (70 mg/dL).
- Pseudo-hypoglycaemia: An episode during which the person with diabetes reports any of the typical symptoms of hypoglycaemia with a measured PG concentration > 3.9 mmol/L (70 mg/dL) but approaching that level.
- Probable symptomatic hypoglycaemia: An episode during which symptoms of hypoglycaemia are not accompanied by a PG determination but that was presumably caused by a PG concentration ≤ 3.9 mmol/L (70 mg/dL).

Note: Glucose measurements are performed with capillary blood calibrated to plasma equivalent glucose values PG: plasma glucose SMPG: Self-measured plasma glucose

Figure 2–2 ADA classification of hypoglycaemia

Treatment emergent hypoglycaemic episodes are presented in terms of the number of subjects with at least one event (N), the percentage of subjects with at least one event (%), the number of events (E) and the event rate per 100 years of exposure (R). Separate summaries are made by severity considering all episodes, nocturnal and daytime episodes using Novo Nordisk and ADA classified episodes. All episodes will also be summarised by category, including summaries in relation to time since start of meal, as occurring within the following time intervals:

- During first 1, 2, and 4 hours after start of meal
- Between 1 (exclusive) to 2 hours (inclusive) after start of meal
- Between 2 (exclusive) to 3 hours (inclusive) after start of meal
- Between 3 (exclusive) to 4 hours (inclusive) after start of meal
- Between 2 (exclusive) to 4 hours (inclusive) after start of meal

The number of treatment emergent severe or BG confirmed hypoglycaemic episodes (all, daytime, nocturnal, 1 hour, 2 hours, 4 hours, 1 (exclusive) to 2 hours (inclusive), 2 (exclusive) to 3 hours (inclusive), 3 (exclusive) to 4 hours (inclusive), and 2 (exclusive) to 4 hours (inclusive) after start of the meal) will be analysed based on the FAS using a negative binomial regression model with a log-link function and the logarithm of the time period in which a hypoglycaemic episode is considered

Statistical Analysis Plan		Date:	12 February 2019	Novo Nordisk
Trial ID: NN1218-4113	CONFIDENTIAL	Version:	2.0	
UTN: U1111-1180-0636		Status:	Final	
EudraCT No.: 2016-000878-38		Page:	25 of 29	

treatment emergent as offset. The model will include treatment, region and metformin use at baseline (Yes/No) as factors. To the extent where data allow, separate analysis will be performed for severe hypoglycaemic episodes (all).

Change from baseline in clinical evaluations 16 weeks after randomisation:

Physical examination

The physical examination parameters (head, ears, eyes, nose, throat, neck, respiratory system, cardiovascular system, gastrointestinal system incl. mouth, musculoskeletal system, central and peripheral nervous system, skin), and their change from baseline, will be summarised descriptively using the on-treatment period. All findings will be listed.

Vital signs

Vital signs include diastolic blood pressure, systolic blood pressure and pulse. The measurements will be summarised descriptively using the on-treatment period and both actual values as mean change and change from baseline.

Electrocardiogram

ECG findings will be summarised descriptively using the on-treatment period and including summaries of the change from baseline. Change from baseline will be summarised as normal/abnormal not clinically significant/abnormal clinically significant categorisation in shift tables.

Fundoscopy/fundus photography

Fundoscopy/fundus photography findings will be summarised descriptively using the on-treatment period and including summaries of the change from baseline. Change from baseline will be summarised as normal/abnormal not clinically significant/abnormal clinically significant categorisation in shift tables.

Change from baseline in clinical laboratory assessments 16 weeks after randomisation

Change from baseline 16 weeks after randomisation in central laboratory assessments:

- Haematology (erythrocytes, haematocrit, haemoglobin, leucocytes, thrombocytes)
- Biochemistry (ALT, AST, albumin, alkaline phosphatase, creatinine, potassium, sodium, total bilirubin, total protein)

Individual laboratory values will be compared to their relevant reference range (when existing) and flagged as being below or above the range. The measurements and their change from baseline will

be summarised descriptively using the on-treatment period. Change from baseline will be summarised both the actual values and the low/normal/high categorisation in shift tables.

Change from baseline in body weight and body mass index 16 weeks after randomisation

The measurements will be summarised descriptively using the on-treatment period and the actual values as mean change.

Change from baseline in body weight will be analysed based on all planned post baseline measurements until or at 16 weeks after randomisation using a statistical model similar to 1) except with the corresponding baseline measurement as covariate. The analysis will be based on the safety analysis set and the on-treatment observation period.

